7.2 Recruitment and screening

We will recruit 30 patients directly at the USZ Allergy Unit. All 30 participants must have a type-1-sensitisation to grass pollen allergens and be undergoing pre-seasonal short-term SCIT scheme with Polvac™ at the USZ Allergy Unit in winter 2023/2024.

Patients will be invited to a screening visit 1 to 60 days before the intervention, where an extensive interview will be conducted and the informed consent will be signed by the patient and the medical investigator. The informed consent will be uploaded to the clinical information system (KISIM) and filed

into the trial master file (TMF). At the screening visit there will be a medical interview assessing all inclusion and exclusion criteria and a short clinical exam (auscultation of the lungs and the heart, blood pressure measurement).

7.3 Assignment to study groups

The 30 patients will be randomized to the two different equally-sized treatment groups (ILIT 400 U and SCIT 2000 U), with each 15 patients per group.

7.4 Criteria for withdrawal / discontinuation of participants

If a patient is seen to be ineligible for study intervention because of change in inclusion or exclusion criteria, the patient may be excluded from the trial at the discretion of the physician. The patient can at any time choose to withdraw the informed consent and thereby be released from the study. Replacement of a study participant is possible if the timeframe of 4-6 weeks between last dose of the short-term scheme and start of the additional allergen injection in the framework of the study can be complied. Replacement of a participant that has withdrawn consent is possible within the time frame of the study.

8. STUDY INTERVENTION

8.1 Identity of Investigational Products

Four weeks after patients have received the full cycle of SCIT with Polvac™ Grass+Rye as a part of standard care treatment, they will be randomized to receive one additional treatment.

All study participants will receive again the same allergen extract (Polvac™ Grass+Rye). Depending on the group allocation, they will receive the allergen by the subcutaneous (SCIT) or by intralymphatic (ILIT) injections.

The following Polvac™ doses are used:

- SCIT (n=15): 0.5 ml Polvac™ (2000 U).
- ILIT (n=15): 0.1 ml Polvac™ (400 U).

8.1.1 Experimental Intervention

The treatment medication (Polvac™ Grass+Rye) will be prepared aseptically as described (Appendix 001). The medication that is stored with the pharma team GCP lab in a temperature-logged fridge (2-8 °C) is placed at room temperature 2 hours prior to use. The medical investigator will order the drug from the pharma team to be provided on the day of treatment or on the day before treatment if treatment will take place early next morning (before 09:00 a.m.). **Table 2** summarizes the characteristics of the Polvac™ Grass+Rye preparation used in standard subcutaneous (SCIT) administration and the experimental intralymphatic (ILIT) administration.

Table 2. Characterisation of Polvac™ Grass+Rye preparation used in standard subcutaneous (SCIT) administration and the experimental intralymphatic (ILIT) administration.

	Polvac Grass+Rye SCIT	Polvac Grass+Rye ILIT
Route of injection	subcutaneous	intralymphatic
Initial U/ml	4000 U/ml	4000 U/ml
Dilution	none	none
Dose volume / injection	0.5 ml	0.1 ml
PhI p 5 / injection	900 ng	180 ng
U / injection	2000	400

To prepare Polvac™ for SCIT (2000 U), the 1 ml medication vial (4000 U/ml) is shaken well for 10 seconds. The head of the vial is disinfected and 0.5 ml of the medication is drawn into a 1 ml syringe with 23G hypodermic needle assuring no air in the syringe or needle. The medication is used no later than 4 hours after the preparation. Replica of the SCIT dose or of the ILIT high dose (see below) are made if more than one injection is to be performed. The remaining medication is discarded. The time

point for preparation is documented in the CRF.

To prepare Polvac™ for ILIT (400 U), the 1 ml medication vial (4000 U/ml) is shaken well for 10 seconds. The head of the vial is disinfected and 0.1 ml of the medication is drawn into a 1 ml syringe with 19G hypodermic needle. The medication is used no later than 4 hours after the preparation. Before injection, the needle is changed to a 23G hypodermic needle, assuring no air in the syringe or needle. Replica of the dose are made if more than one ILIT is to be performed, and the remaining medication is discarded. The time point for preparation is documented in the drug accountability log (Appendix 004).

Commercially available Polvac™ will be purchased from Bencard AG (Greifensee, Switzerland) and kept in a temperature-logged fridge (2-8 °C).

After preparation of the syringes, these will be labelled with the study name (ILIT-FNA-2023), patient number, and the expiry time point (e.g., "ILIT-FNA-2023, #21, Exp 21.12.23, 10:30h").

8.1.2 Control Intervention (standard/routine/comparator treatment)

No control intervention is used in this study.

8.1.3 Packaging, Labelling and Supply (re-supply)

All medication is stored in a temperature-logged fridge with the pharma team GCP lab at the Department of Dermatology.

The medical investigator will request needed medication from the pharma team at the Department of Dermatology.

The treatment medication will be prepared aseptically under laminar flow between 30 minutes and 4 hours before use. After preparation, the medication is discarded or it is stored in a temperature-logged fridge with the pharma team at the Department of Dermatology.

The IMP Polvac™ has market authorization (MA) and has been released for the market. However, as the IMP Polvac™ will be administrated in different doses for the study, a simplified Investigator Medicinal Product Dossier (sIMPD) is provided (Appendix 003). The drug substance remains unchanged.

8.1.4 Storage Conditions

Polvac™ will be kept in a temperature-logged fridge (2-8 °C) in the Department of Dermatology. The medication is collected and brought to room temperature at least 30 minutes and not longer than 4 hours before administration.

The time points for removal of medication from fridge and the administration time are documented in a drug accountability log (one for all patients).

8.2 Administration of experimental and control interventions

8.2.1 Experimental Intervention

8.2.1.1 Allergen Injection

The immunotherapy is performed by an experienced physician at the USZ Circle Allergy Unit (Department of Dermatology). Both SCIT and ILIT injections are performed using 1 ml syringes with 23G needles and for both SCIT and ILIT, inguinal lymph nodes are identified using ultrasound guidance. For SCIT, a volume of 0.5 ml undiluted Polvac™ is injected subcutaneously ca. 1 cm from a lymph node (**Fig. 3**). For ILIT a volume of 0.1 ml undiluted Polvac™ is injected directly into a lymph node. The lymph nodes are tagged by marking the site of injection, ultrasound position and video recording of injection with the ultrasound machine.

[figure not shown]
[figure not shown]

Figure 3: By ILIT administration, the study drug is injected into an inguinal lymph node under ultrasound guidance (top image), which allows targeting of the needle to the lymph node (lower left). In the current study, the study drug, Polvac™ Grass+Rye, is injected into an inguinal lymph node (ILIT) or it is injected subcutaneously ca. 1 cm from an inguinal lymph node (SCIT) is illustrated in the scheme (lower right). Two, six or 24 hours after injection, a fine-needle aspiration (FNA) of the treated (LIT) or involved (SCIT) LN is performed. As baseline control, the contralateral LN is also aspirated (green dot).

8.2.1.2 *Fine needle aspiration (FNA)*

The FNA is minimally invasive and an alternative to more invasive methods such as incisional or excisional biopsy for sampling of lymph node tissue (Fig. 3). Just recently, we used FNA in a similar way on sentinel lymph nodes in skin cancer patients (44).

An experienced investigator will perform the FNA. The skin above the lymph node, will be disinfected and a sterile needle (23-25g), attached to the 5 ml syringe, fixed in a FNA gun, will be inserted into the lymph node cortex under colour Doppler ultrasound guidance while avoiding important tissues and organs, such as large blood vessels and nerves. The syringe plunger is drawn to set the seal at a 2 ml scale in order to maintain negative pressure in the syringe. After rotating and aspirating the syringe 5 times, the needle is rotated to aspirate in a fan shape way at different trajectories in the lymph node. The needle is withdrawn when ca. 0.1 ml tissue is present in the syringe. The puncture site is covered with sterile gauze and pressure is applied with appropriate force for 10 min. Patients are observed for 30 min of observation and released when no adverse reaction.

The FNA sample will be rinsed with dimethyl sulfoxide (DMSO)-containing live cell freezing medium (10% DMSO and 90% fetal bovine serum (FBS)), put into a cryotube and frozen in -80°C.

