6.2 Methods of minimising bias

6.2.1 Randomisation

All patients who give consent for participation and who fulfil the inclusion criteria will be randomized to either SCIT or ILIT treatment group with a 1:1 allocation. The randomisation list will be computer-generated by a statistician using a permuted block design (groups of six). Before trial initiation, randomisation envelopes will be given to the study physician who will then be responsible of envelope storage and appropriate use. Allocation concealment will be ensured as the randomisation envelopes will not be opened before the patient has been recruited into the trial, which takes place after screening has been completed.

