6.2.2 Blinding procedures

Not applicable. The study is not blinded.

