9.3.3 Visit 3 (30 minutes)

Completed until 04.02.2024 (2, 6 or 24 hours after SCIT/ILIT))

- Venous blood collection before injection (5 ml serum and 25 ml EDTA)
- FNA of ILIT-treated inguinal lymph node or lymph node adjacent to SCIT injection
- FNA of non-involved inguinal lymph node on the opposite side, which had not been treated (baseline measurement)

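### Only the arm is randomised, and no rule is stated for the injected side or the node, so the within-patient lymph-node contrast is open to node-selection bias

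*Combined protocol and SAP*

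**What the plan says.** Section 6.2.1 has patients "randomized to either SCIT or ILIT treatment group with a 1:1 allocation", in blocks of six. Sections 6.2.3 and 7.3 likewise speak only of two treatment groups. Neither the side nor the node is part of the allocation.

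On timing, "the randomisation envelopes will not be opened before the patient has been recruited into the trial". The study schedule (Table 1) puts randomisation at Visit 1 and the injection at Visit 2. Section 6.2.2 on blinding reads "Not applicable. The study is not blinded".

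At the injection, section 8.2.1.1 states that "for both SCIT and ILIT, inguinal lymph nodes are identified using ultrasound guidance". The ILIT needle enters the node; the SCIT injection is placed about 1 cm from one. The same section adds: "The lymph nodes are tagged by marking the site of injection, ultrasound position and video recording of injection". It describes no tagging of the reference node.

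The reference is defined in section 9.3.3 (and 9.3.2) as "FNA of non-involved inguinal lymph node on the opposite side, which had not been treated (baseline measurement". Section 6.1 has it aspirated together with the treated node, 2, 6 or 24 hours after the injection. No matching on size or position is described.

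The lymph-node part of the primary outcome (5.1) is the change from this baseline. The primary objective (4.2) is ILIT versus SCIT, in blood and lymph nodes.

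**The concern.** A within-patient comparison of two nodes isolates the drug effect only if the treated node and its reference would have looked alike on average without the drug. Randomising the arm does not secure that. It makes the two groups of patients comparable, not the two groins of one patient.

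If the injected node tends to be, say, the larger or the easier one to reach, and that feature is related to cell composition or function, part of the treated-minus-contralateral difference existed before the injection. No pre-injection aspirate is planned that could separate the two. Section 11.1 gives describing the effect of ILIT on cells in lymph nodes as a goal, so the within-ILIT node contrast matters in its own right. According to section 3.1, the results should also inform larger studies.

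**Working it through.** **The plan's own figures.** There is no sample-size calculation to reproduce: the synopsis and section 11.2 give no alpha, power, effect size or SD. The allocation arithmetic of the body fits: 30/6 = 5 full blocks, 15 per arm. (The synopsis speaks of three groups of 10. The body's two groups of 15 are used here.)

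**What protects each contrast**

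| Contrast | Protection in the text |
|---|---|
| Blood, change over time | Pre-injection sample (8.2.1.3) |
| Node, treated v contralateral | None stated for side or node |
| Node, ILIT v SCIT | Arm randomised; a selection rule common to both arms cancels in expectation if effects are additive |

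**Assumed inputs.** Let b be the pre-existing difference between the treated and reference node, in SDs of the paired difference, with no drug effect. The documents give no value, so b runs from 0.08 to 0.5. Tests are two-sided at 5%. Fifteen pairs means pooling the 2, 6 and 24 hour samples; 5 pairs assumes an equal split, 15/3. The protocol states neither.

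**Formulas.** The paired test follows a noncentral t with n − 1 df and noncentrality b√n. For the two-arm test with the bias in ILIT only, df = 28 and noncentrality is b√(15/2).

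For b = 0.5: 0.5 × √15 = 1.94 (14 df), 0.5 × √5 = 1.12 (4 df) and 0.5 × √7.5 = 1.37 (28 df). The false-positive rates are:

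| b | Paired, 15 pairs | Paired, 5 pairs | 15 v 15, bias in ILIT only |
|---|---|---|---|
| 0.08 | 6.0% | 5.2% | 5.5% |
| 0.3 | 19.2% | 8.2% | 12.5% |
| 0.5 | 43.8% | 14.1% | 26.2% |

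**What b requires.** Take two independent, standard normal nodes per patient. The node with the larger value of some feature is always injected, and rho is the correlation of that feature with the read-out. The expected difference is rho × 2/√π = 1.128 rho node SDs. Dividing by √2 gives b = 0.80 rho. So b = 0.08 needs rho = 0.1, b = 0.3 needs about 0.38 and b = 0.5 about 0.63.

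**Simulation of that model** (100,000 trials, no drug effect):

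| rho | Paired, 15 pairs | Paired, 5 pairs | 15 v 15, same rule in both arms | 15 v 15, rule in ILIT only |
|---|---|---|---|---|
| 0.1 | 5.9% | 5.1% | 5.2% | 5.5% |
| 0.3 | 14.4% | 7.2% | 5.0% | 9.9% |
| 0.5 | 34.9% | 11.5% | 5.0% | 19.6% |

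At rho = 0 every rate is about 5%. With the side drawn at random between two fixed candidate nodes, the expected bias is 0 and the paired rate stays at 4.9% to 5.1% for every rho tried.

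**The case against.** A reader might infer that the operator picks the groin, that the node contrast therefore carries bias, and that this bias does not cancel between the arms. The documents support none of these as a flat statement.

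- **Operator choice is inferred from silence.** The sentence in 8.2.1.1 shows only that ultrasound is used. Figures 2 to 4 and the CRF (Appendix 005) are not available here, and a side rule could stand there.
- **Bias needs two conditions:** selection on some feature, and a link between that feature and the read-out. The documents establish neither. Section 7.1 excludes patients with conspicuous nodes, which narrows the differences without removing them.
- **ILIT-only selection is an extreme case.** The routes do set different needle targets. But in both arms the treated or draining node and the contralateral node are later entered for aspiration (8.2.1.2), so SCIT also needs accessible nodes. A rule common to both arms leaves ILIT versus SCIT at about 5%.
- **The upper rates are not typical.** They need a moderate to strong link, consistent selection and pooled time points.
- **This is a descriptive pilot** with no single primary endpoint, and the paired t-test is optional (11.4).

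All of this limits the claim and its size. It does not remove the gap: no stated rule protects the node contrast. Nor is a descriptive purpose a full defence, because section 11.4 lists comparative tests and a biased contrast misleads a description too.

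**Conclusion.** The point holds in conditional form. The readable text randomises the arm only and gives no rule for the side or the node, and the arm is known when nodes are located. The within-patient node contrast is therefore open to selection bias. ILIT versus SCIT is affected only if node choice differs by route. The blood outcomes are not affected.

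The size is unknown. Over the assumed range, inflation runs from negligible to large, and it is much smaller if time points are analysed separately. The harm would be a misleading description of some lymph-node read-outs, not the loss of a confirmatory error rate. Confidence is high that the readable text lacks the safeguard and moderate at most on the size of any bias. The change is worth making because it costs so little.

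**What to change.** - **8.2.1.1:** before the side is revealed, identify one candidate node in each groin by one written rule, and record its size and position. The same two nodes are aspirated later. Fixing them first matters: a random side alone would still leave a choice among several nodes within a groin.
- **6.2.1:** add the injected side (left/right, 1:1, balanced within arm) to the randomisation list, in a sealed part opened only after both nodes are recorded. A block of six holds three patients per arm, so balance has to be set over the whole list (8 v 7 in each arm of 15).
- **Switches:** allow one only if no suitable node can be imaged on the assigned side, and record the reason.
- **11.4:** analyse the node contrast by the side actually injected, since analysing a switched patient by assigned side would label an uninjected node as treated. Report all switches, and add a sensitivity analysis without switched patients.

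Cost: one column in the list, a few sentences, and a short imaging record of both groins. No extra patients or needle procedures are needed. The operator will sometimes work on the less convenient side. If a side or node rule already exists in the figures or the CRF, state it in 8.2.1.1.

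This does not cure the fact that the baseline node is sampled after the injection, which is a separate issue.

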8.2.1.3 Blood collection and preservation of cells and blood serum

First venous blood collection is performed at baseline before the immunotherapy. Second blood collection is performed 2, 6 or 24 hours post injection. Third and fourth blood collection are performed 7 and 28 days after immunotherapy. Each time, 25 ml venous blood is collected for preparation of PBMCs and 5 ml blood is collected for preparation of serum. Both samples are processed by routine in-house methods within 2 hours for preparation of serum and cells. The produced serum is aliquoted in 1 ml samples and frozen at – 20 °C for later analysis. Whole blood is centrifuged on Ficoll and the PBMCs isolated and washed in PBS before re-suspended in DMSO-containing live cell freezing medium. 1 ml aliquots of the cells are slow-frozen in cryotubes and finally stored at -80 °C before further analysis.

8.2.2 Control Intervention

No control intervention is used in this pilot study.

8.3 Dose modifications

We already have experiences with dosing Polvac™ from an ongoing study using Polvac™ at our department (BASEC Number: 2021-02301) and with off-label use of up-dosing Polvac™. The ILIT doses used in the trial described in the current protocol is based on the experience from the past trial (133 U) and from off-label treatment of four patients in February to April 2023 (133 U, 200 U and 400 U).

We inject the study dose after patients finished a full cycle of pre-seasonal short-term SCIT scheme with Polvac™ (the patients have therefore reached and tolerated the maximal maintenance dose of 2000 U). The maximal dose in the current study will not exceed the maintenance dose for SCIT (2000 U) and will be much lower for ILIT (400 U) and should therefore be well tolerated by the study participants.

8.4 Compliance with study intervention

Monitoring of subject compliance will not be done. We only include patients who have finished pre-seasonal SCIT with six injections at the USZ Allergy Unit. Patients who opt for SCIT are usually highly motivated because their burden of allergy-suffering is high. The effort for the patient associated with our study is relatively modest. The five personal visits include 1) screening visit (which can be combined with a SCIT injection already planned), 2) allergen injection, 3) FNA and blood samplings 2-24 hours post injection, 4) follow-up after 7 days, and 5) follow-up after 28 days. We expect that the patients will be motivated for the study, because they potentially will benefit from this one additional injection and might also benefit from future ILIT applications (such as off-label interventions).

8.5 Data Collection and Follow-up for withdrawn participants

In accordance with the Declaration of Helsinki, the investigator must explain to the patient that they have the right to withdraw from the study at any time, and that this will in no way prejudice their future treatment. We are required by law to report on adverse events and other side effects; this law takes precedence over the GDPR as it concerns public safety. Even if a patient withdraws from the project, we will have to keep safety data after treatment. However, all other clinical data that do not relate to safety of the applied treatment, will be deleted at a written request of a patient. A subject that discontinues will always be asked about the reason(s) for discontinuation and the presence of any adverse events. The timing and reason for any kind of withdrawal will be recorded in the patient medical file (KISIM) and deposited in the TMF. The sponsor should inform Swissmedic and IEC within 24 hours after decision of a treated patient to discontinue the study and also the consequences for the study persons as well as for the continued investigations will be declared.

Intervention (SCIT or ILIT) within the study is not necessary for the routine therapy for the patients, therefore, the study intervention don't need to be repeated in case of a withdrawal.

8.6 Trial specific preventive measures

All the preventive measures described below will be recorded in the CRF.

Prior to the allergen injection, a pregnancy testing (if applicable) will be performed.

The patients will receive an emergency set ("Allergie Notfallset") to take home in case of systemic side effects (Appendix 003). The emergency set consists of two tablets of Xyzal® 5 mg (Levocetirizine dihydrochloride) and two tablets of Spiricort® 50 mg (Prednisolone). Patients will be given an instruction about when and how to use the emergency set. Fenistil gel 1% will be given for local allergic reactions restricted to the site of injection.

After ILIT treatment the patients have to stay one hour at the allergy unit for observation.

During the study (from allergen injection to blood samplings after 28 d) patients cannot receive another allergen injection. To avoid allergen exposure from the environment, the study allergen is seasonal, and therefore not in the environment during the whole study period.

8.7 Concomitant Interventions (treatments)

Besides the allergen administration (via ILIT or SCIT), the FNA (2x) and blood collection (4x) a pregnancy test, 2x peak flow measurement and a physical examination will be performed.

